9.6.1.3 Estimation of Percent Seroconversion and Percent Seroresponse

The seroconversion percentages with respect to HPV Types 6, 11, 16, 18, 31, 33, 45, 52, and 58, and seroresponse percentage with respect to SARS-CoV-2, will be evaluated by computing point estimates and corresponding 2-sided 95% CIs. Calculation of the CI will be based on the exact binomial method proposed by Clopper and Pearson [CLOPPER, C. J. and PEARSON, E. S. 1934] ([Table 9](#)).

Table 9 Strategy for Analysis of Immunogenicity Endpoints

Endpoint/Variable (Description, Time Point)	Primary vs. Supportive Approach	Statistical Method	Analysis Population	Missing Data Approach
Primary Immunogenicity Objectives and Hypotheses				
GMTs of anti-HPV 6, 11, 16, 18, 31, 33, 45, 52, and 58 measured by cLIA at 4 weeks Postdose 2 of 9vHPV vaccine	P	Point estimate, 95% CI by ANOVA	Per-protocol	Observed data only
GMCs of SARS-CoV-2 spike protein-specific binding antibodies at 4 weeks Postdose 2 of mRNA-1273 vaccine	P	Point estimate, 95% CI by ANOVA	Per-protocol	Observed data only
Secondary Immunogenicity Objectives				
Seroconversion to HPV Types 6, 11, 16, 18, 31, 33, 45, 52, and 58 at 4 weeks Postdose 2 of 9vHPV vaccine	P	Point estimate, 95% CI value by Clopper and Pearson	Per-protocol	Observed data only
Seroresponse to SARS-CoV-2 at 4 weeks Postdose 2 of mRNA-1273 vaccine	P	Point estimate, 95% CI value by Clopper and Pearson	Per-protocol	Observed data only
ANOVA=analysis of variance; CI=confidence interval; cLIA=competitive Luminex Immunoassay; GMC=geometric mean concentration; GMT=geometric mean titer; HPV=human papillomavirus; P=primary; RNA=ribonucleic acid; SARS-CoV-2=severe acute respiratory syndrome coronavirus 2				

9.6.2 Safety Analysis Methods

Safety and tolerability will be assessed by clinical review of all relevant parameters, including AEs and postvaccination body temperature measurements.

The analysis of safety results will follow a tiered approach ([Table 10](#)). The tiers differ with respect to the analyses that will be performed. AEs (specific terms as well as system organ class terms) are either prespecified as “Tier 1” endpoints or will be classified as belonging to “Tier 2” or “Tier 3” based on the observed number of participants with an event.

Tier 1 Events

Safety parameters or AEs of special interest identified *a priori* that will be subject to inferential testing for statistical significance constitute “Tier 1” safety endpoints. There are no Tier 1 events for this protocol.

Tier 2 Events

Tier 2 parameters will be assessed via point estimates with 95% CIs provided for differences in the proportion of participants with events using the M&N method [Miettinen, O. and Nurminen, M. 1985]. Membership in Tier 2 requires that at least 4 participants in any vaccination group exhibit the event. The threshold of at least 4 participants was chosen because the 95% CI for the between-group difference in percent incidence will always include zero when vaccination groups of equal size each have less than 4 participants and thus would add little to the interpretation of potentially meaningful differences. The 95% CIs for Tier 2 events will be provided without adjustment for multiplicity, thus the CIs should be regarded as a helpful descriptive measure to be used in review, not a formal method for assessing the statistical significance of the between-group differences with respect to the Tier 2 events.

In addition to individual events that occur in ≥ 4 participants in any vaccination group, the broad AE categories consisting of the proportion of participants with SAEs during Days 1 through 28 postvaccination, AEs of special interest (see Section 10.3.1), MAAEs, and vaccine-related SAEs reported any time during the study, and elevated temperatures ($\geq 37.8^{\circ}\text{C}$ or $\geq 100.0^{\circ}\text{F}$) will be considered Tier 2 endpoints. The proportion of participants with solicited injection-site AEs and solicited systemic AEs during Days 1 through 7 postvaccination, and severe injection-site AEs during Days 1 through 28 postvaccination will also be included in Tier 2 endpoints. Detailed endpoints and day ranges are summarized in [Table 10](#).

The day ranges (Days 1 through 7 and Days 1 through 28) associated with some Tier 2 endpoints are consistent with those used in clinical studies of the mRNA-1273 vaccine.

Tier 3 Events

Safety endpoints that are not Tier 2 events are considered Tier 3 events. Only point estimates (counts and percentages) by vaccination group are provided for Tier 3 safety parameters. Safety analyses will be based on the observed data (ie, with no imputation of missing data).

The day ranges (Days 1 through 5 and Days 1 through 15) associated with some Tier 3 endpoints are consistent with those used in clinical studies of the 9vHPV vaccine. Summaries for these endpoints are planned to be provided for comparability with summaries in previous 9vHPV vaccine clinical studies.

Table 10 Strategy for Analysis of Safety Endpoints

Safety Tier	Safety Endpoint ^a	95% CI for Comparison of Concomitant and Nonconcomitant Groups	Descriptive Statistics
Tier 2	Solicited injection-site AEs, Days 1 through 7 postvaccination	X	X
	Severe injection-site AEs, Days 1 through 28 postvaccination	X	X
	Unsolicited injection-site AEs observed in ≥ 4 participants in either vaccination group, Days 1 through 28 postvaccination	X	X
	Solicited systemic AEs (headache, fatigue, myalgia, arthralgia, nausea, vomiting, and chills), Days 1 through 7 postvaccination	X	X
	Unsolicited systemic AEs observed in ≥ 4 participants in either vaccination group, Days 1 through 28 postvaccination	X	X
	Elevated temperatures ^a , Days 1 through 7 postvaccination	X	X
	Serious AEs, Days 1 through 28 postvaccination	X	X
	Serious vaccine-related AEs reported any time during the study	X	X
	AEs of special interest reported any time during the study	X	X
	MAAEs reported any time during the study	X	X
Tier 3	Solicited injection-site AEs, Days 1 through 5 postvaccination		X
	Severe injection-site AEs, Days 1 through 15 post vaccination		X
	Unsolicited injection-site AEs observed in ≥ 4 participants in either vaccination group, Days 1 through 15 postvaccination		X
	Systemic (solicited or unsolicited) AEs observed in ≥ 4 participants in either vaccination group, Days 1 through 15 postvaccination		X
	Elevated temperatures ^a , Days 1 through 5 postvaccination		X
	Serious AEs, Days 1 through 15 postvaccination		X
	AEs by SOC		X
	Maximum intensity rating for each category of injection-site AEs		X
	Maximum intensity rating, overall systemic AEs		X
	Maximum temperatures		X

AE=adverse event; CI=confidence interval; MAAE=medically attended adverse event; SOC=system organ class; X=indicating summary statistic will be provided

^a Defined as maximum (over the follow-up period) temperature $\geq 37.8^{\circ}\text{C}$ ($\geq 100^{\circ}\text{F}$, oral equivalent).

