The classification of IMP and NIMP/AxMP in this table is based on guidance issued by the European Commission and applies to countries in the European Economic Area (EEA). Country differences with respect to the definition/classification of IMP and NIMP/AxMP may exist. In these circumstances, local legislation is followed.

* mRNA encoding the prefusion stabilized spike glycoprotein of SARS-CoV-2 virus (Moderna Inc., Cambridge, MA)

Other current or former name(s) or alias(es) for study intervention(s) are as follows: Moderna COVID-19 vaccine and mRNA-1273 SARS-CoV-2 vaccine for mRNA-1273 vaccine; GARDASIL®9 and V503 for 9vHPV vaccine.

Total Number of Intervention Groups/Arms	2 intervention groups
Duration of Participation	Each participant will participate in the study for approximately 7 or 9 months from the time the participant provides documented informed consent/assent through the final contact.

Study Governance Committees:

Executive Oversight Committee	No
Data Monitoring Committee	No
Clinical Adjudication Committee	No

There are no governance committees in this study.

[figure not shown]
Study Accepts Healthy Participants: Yes

A list of abbreviations is in Appendix 8.

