1.3 Schedule of Activities

1.3.1 Scheduled Visits for Concomitant Group

Study Period	Intervention and Follow-up					Notes
Visit Number	1	2	3	4a	5a	
Scheduled Time	Day 1	Month 1	Month 2	Month 6	Month 7	
Visit Window ^a		28 to 42 days after Visit 1	28 to 42 days after Visit 2	6 months after Day 1 ±4 weeks	28 to 49 days after Visit 4a	To calculate visit windows, assume 1 month = 30 days and 1 week = 7 days.
Administrative and General Procedures						
Obtain Informed Consent/Assent	X					The interval between the date of consent and the date of the Day 1 visit should be no more than 14 days. If the interval is ≥15 days, then the participant must be reconsented.
Obtain Informed Consent/Assent for Future Biomedical Research	X					Participation in future biomedical research is optional and consent/assent must be obtained before collection of blood (DNA) samples.
Review Inclusion/Exclusion Criteria	X					
Assign Participant Identification Card	X					
Collect Medical History	X					See Section 8.1.4 for details.
Collect Demographics	X					
Review Prior/Concomitant Medication and Nonstudy Vaccination	X	X	X	X	X	See Section 8.1.6 for details.
Clinical Procedures and Assessments						
Measure Oral Temperature	X	X		X		Oral temperature should be measured prior to vaccination. If the participant has a fever within the 24-hour period prior to a vaccination visit, the visit should be rescheduled until after the fever has resolved (Section 5.2).
Record Height and Weight	X					Height and weight will be recorded on Day 1 before vaccination.
Perform Physical Examination	X					Performed at Day 1 to assess inclusion/exclusion criteria. After Day 1, a physical examination is optional.

Study Period	Intervention and Follow-up					Notes
Visit Number	1	2	3	4a	5a	
Scheduled Time	Day 1	Month 1	Month 2	Month 6	Month 7	
Visit Window ^a		28 to 42 days after Visit 1	28 to 42 days after Visit 2	6 months after Day 1 ±4 weeks	28 to 49 days after Visit 4a	To calculate visit windows, assume 1 month = 30 days and 1 week = 7 days.
Laboratory Procedures and Assessments						
Perform Pregnancy Testing, Serum or Urine (required for all females)	X	X		X		The serum pregnancy test or urine pregnancy test must be sensitive to at least 25 mIU/mL β-hCG and performed prior to vaccination. Results must be negative prior to vaccination (Section 8.3.6).

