8.4 Adverse Events, Serious Adverse Events, and Other Reportable Safety Events

The definitions of an AE or SAE, as well as the method of recording, evaluating, and assessing causality of AE and SAE and the procedures for completing and transmitting AE, SAE, and other reportable safety event reports can be found in Appendix 3.

Adverse events, SAEs, and other reportable safety events will be reported by the participant (or, when appropriate, by a caregiver, surrogate, or the participant's legally authorized representative).

The investigator and any designees are responsible for detecting, documenting, and reporting events that meet the definition of an AE or SAE as well as other reportable safety events. Investigators remain responsible for following up AEs, SAEs, and other reportable safety events for outcome according to Section 8.4.3.

The investigator, who is a qualified physician, will assess events that meet the definition of an AE or SAE as well as other reportable safety events with respect to seriousness, intensity/toxicity, and causality.

8.4.1 Time Period and Frequency for Collecting AE, SAE, and Other Reportable Safety Event Information

All AEs, SAEs, and other reportable safety events that occur after the participant provides documented informed consent/assent, but before allocation/randomization, must be reported by the investigator if they cause the participant to be excluded from the study, or are the result of a protocol-specified intervention, including, but not limited to washout or discontinuation of usual therapy, diet, placebo, or a procedure.

All AEs that occur from the time of allocation/randomization through 28 days following the first vaccination(s) and from the time of any subsequent vaccination(s) through 28 days thereafter, must be reported by the investigator. All MAAEs, SAEs, and other reportable safety events that occur from the time of allocation/randomization throughout the duration of the individual's participation in the study, must be reported by the investigator, regardless of whether the events are considered to be vaccine-related by the investigator.

In this study, myocarditis and pericarditis are always considered to be SAEs that meet the "Other important medical events" criteria detailed in Section 10.3.2 (the investigator should also assess whether other criteria might apply). Definitions of myocarditis and pericarditis are provided in Section 10.3.1.

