9.12 Extent of Exposure

The extent of exposure will be summarized by the number and proportion of study participants administered the 9vHPV vaccine and mRNA-1273 vaccine.

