- Anticipated day-to-day fluctuations of preexisting disease(s) or condition(s) present or detected at the start of the study that do not worsen.
- Surgical procedure(s) planned prior to informed consent to treat a preexisting condition that has not worsened.
- Refer to Section 8.4.6 for protocol-specific exceptions.

Definition of Solicited and Unsolicited AE

- Solicited AEs are predefined local (at the injection site) and systemic events for which the participant is specifically questioned, and which are noted by the participant in their VRC.
- An unsolicited AE is an AE that was not solicited using a VRC and that is communicated by a participant who has provided documented informed consent/assent. Unsolicited AEs include serious and nonserious AEs.

Definition of MAAE

- AEs in which medical attention is received during an unscheduled, nonroutine outpatient visit, such as an emergency room visit, office visit, or an urgent care visit with any medical personnel for any reason. Routine visits are not considered MAAEs. Examples of routine visits include physical examination, wellness visits, or vaccinations.
- Note: Determination of MAAEs is the responsibility of the investigator or a qualified designee. Once identified, MAAEs should be reported to the Sponsor per the timeline for NSAE/SAEs reporting.

Definition of AEs of Special Interest

- AEs of special interest (serious and nonserious AEs) for this study are scientific and medical concerns specific to the mRNA-1273 vaccine per regulatory requirements. The list of AEs of special interest is provided below.

Medical Concept	Additional Notes
Anosmia, ageusia	New onset COVID-associated or idiopathic events without other etiology excluding congenital etiologies or trauma.
Subacute thyroiditis	Including but not limited to events of atrophic thyroiditis, autoimmune thyroiditis, immune-mediated thyroiditis, silent thyroiditis, thyrotoxicosis, and thyroiditis.
Acute pancreatitis	
 • Including but not limited to events of autoimmune pancreatitis, immune-mediated pancreatitis, ischemic pancreatitis, edematous pancreatitis, pancreatitis, acute pancreatitis, hemorrhagic pancreatitis, necrotizing pancreatitis, viral pancreatitis, and subacute pancreatitis. • Excluding known etiologic causes of pancreatitis (alcohol, gallstones, trauma, recent invasive procedures).
Appendicitis	Include any event of appendicitis.

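### Table 10 compares raw any-time MAAE proportions although follow-up is about 7 months in one group and 9 in the other, which tilts the expected difference towards the Concomitant Group

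*Combined protocol and SAP*

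**What the plan says.** Section 9.6.2 assesses Tier 2 endpoints by "point estimates with 95% CIs provided for differences in the proportion of participants with events using the M&N method". Table 10 lists "MAAEs reported any time during the study" as a Tier 2 row with a between-group 95% CI, and treats "AEs of special interest reported any time during the study" and vaccine-related SAEs over the whole study in the same way.

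Collection runs over each participant's own time in the study. Section 8.4.1 covers "All MAAEs, SAEs, and other reportable safety events that occur from the time of allocation/randomization throughout the duration" of that participation, regardless of the investigator's view of relatedness. The MAAE definition in Section 10.3.1 includes "an urgent care visit with any medical personnel for any reason"; only routine visits are excepted.

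That time differs by assignment. The Synopsis states: "Each participant will participate in the study for approximately 7 or 9 months". In Section 1.3.1 the second 9vHPV dose falls "6 months after Day 1 ±4 weeks" and the final visit is Month 7. In Section 1.3.2 the 9vHPV series starts only at Visit 3, so the final visit is Month 9.

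Nothing in Section 9 gives person-time, a common cut-off or a time-to-event method for these rows. On exposure, Section 9.12 says only: "The extent of exposure will be summarized by the number and proportion of study participants administered" each vaccine. Section 9.6.2 calls the Tier 2 intervals descriptive and unadjusted, and Section 9.4.2 does not list MAAEs among the four endpoints that address the primary safety objective.

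**The concern.** In healthy children aged 9 to 11, many unscheduled medical visits can be expected to follow calendar time rather than vaccine doses. A group watched for two more months will then have more participants with at least one MAAE, even if vaccination timing has no effect. The planned difference mixes any real effect with a difference in observation time that the design itself creates.

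The direction matters because Objective 3 is the safety of concomitant first doses. A reader could take shorter follow-up for a safety advantage. In the other direction, a moderately higher true MAAE rate in the Concomitant Group could be offset by its shorter follow-up and leave no visible difference.

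**Working it through.** **Check of the method.** Section 9.6.2 says that with equal groups and fewer than 4 events in each, the 95% CI always includes zero. The Miettinen-Nurminen (M&N) interval at 80 per group agrees at the most extreme case: 3 vs 0 gives -0.9 to 10.5 points. At 4 vs 0 it gives +0.3 to 12.2 and excludes zero.

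**Follow-up** (Sections 1.3.1 and 1.3.2; 1 month = 30 days, 1 week = 7 days).

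- Concomitant: nominal 180 + 30 = 210 days. Within windows, (180 - 28) + 28 = 180 to (180 + 28) + 49 = 257.
- Nonconcomitant: nominal 60 + 180 + 30 = 270 days. Within windows, 56 + 152 + 28 = 236 to 84 + 208 + 49 = 341.
- The 9vHPV dose interval and the final-visit window are the same in both groups. At equal window positions the extra time is therefore Day 1 to Visit 3: 28 + 28 = 56 to 42 + 42 = 84 days. The ranges overlap, so individual differences vary more widely.

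**Expected difference with no true effect.** The documents give no MAAE rate, so the monthly rate r is an assumption: constant and equal in both groups. The proportion with at least one event is 1 - exp(-7r) vs 1 - exp(-9r). As a sensitivity check, participants may differ in their underlying rate (gamma frailty, variance v = 2), which gives 1 - (1 + v·r·T)^(-1/v) at T months. At r = 0.05 that is 1 - 1.7^(-1/2) = 23.3% vs 1 - 1.9^(-1/2) = 27.5%. Differences are taken before rounding.

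| Assumed rate per month | Concomitant | Nonconcomitant | Difference (points) | Difference with frailty |
|---|---|---|---|---|
| 1% | 6.8% | 8.6% | -1.8 | -1.6 |
| 2% | 13.1% | 16.5% | -3.4 | -2.6 |
| 5% | 29.5% | 36.2% | -6.7 | -4.1 |

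Under equal constant rates the sign is negative at every rate above zero.

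**Size against noise, 80 per group.** M&N intervals on whole counts near expectation are -11.6 to 6.3 points (5 vs 7), -15.1 to 7.4 (10 vs 13) and -20.6 to 8.4 (24 vs 29). All span zero. Enumerating all 81 × 81 outcomes gives the chance that the interval lies wholly below zero with no true effect: 5.8%, 8.5% and 14.6% at the three rates (5.2%, 7.0% and 8.6% with frailty). With 9 months in both groups it is 2.3 to 2.5%.

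**Offset.** If the Concomitant rate is (9/7)r = 1.29r, then 1 - exp(-7 × (9/7)r) = 1 - exp(-9r), so the expected planned difference is zero. Over an equal 7 months the true difference would be +1.8, +3.4 or +6.7 points.

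**AEs of special interest.** At an assumed 0.2% per month: 1.4% vs 1.8%, or -0.4 points, about 1.1 vs 1.4 participants of 80.

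**Check of the remedy.** In 40,000 simulated trials with no true effect and no frailty, the difference in first-event rates averaged 0.00 to -0.01 per 100 person-months. A Wald interval had uneven tails (2.8 to 2.9% wholly below zero, 1.7 to 2.2% wholly above), so the interval method should be chosen and named. With frailty, the rates at 5% were 3.9 vs 3.7, a small shift the other way. For a purely dose-driven event (assumed 2% per dose, 4 doses in each group), the proportion is 1 - 0.98^4 = 7.8% in both groups. Dividing by full participation gives 7.8/7 = 1.1 vs 7.8/9 = 0.9 per 100 person-months, so the rate over-corrects such events.

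**The case against.** The strongest reply is that little depends on this row. The study has no hypothesis test, the intervals are declared descriptive, MAAEs are supportive, and the 7 and 9 months are stated openly in the Synopsis. Shifts of 1.8 to 6.7 points sit inside interval half-widths of about 9 to 14.5. All of this stands, and it limits the consequence to interpretation. It does not remove the point: in an estimation study the estimates are the product, and this one has a direction set by the visit schedule.

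A second reply is that the size is assumed. That also stands. An adverse event is defined by its timing relative to the intervention, and the broad wording in the MAAE definition describes the medical visit. Some MAAEs will follow doses, of which each group has four, and that share shrinks the shift. Strong seasonality could change its size or even its direction, and would affect a person-time rate as well.

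Some stronger readings are tempting. A reader might infer that the trial is likely to show a spurious safety advantage; the intervals above do not support that. A reader might infer that adverse events of special interest need the same treatment; if they are rare, the shift is negligible and a rate interval on about one event per group would be uninformative. A reader might also infer that the primary safety results are compromised. The primary endpoints with a fixed number of days after vaccination do not run on the 7 vs 9 month clock. Vaccine-related SAEs do, but the relatedness requirement limits the effect, so a footnote is enough there.

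**Conclusion.** The point holds for MAAEs. As written, the plan yields a between-group MAAE difference that is expected to favour the Concomitant Group when background rates are equal and constant, and nothing in the documents adjusts for this or labels it. The expected shift is -1.8 to -6.7 points for assumed rates of 1 to 5% per month, or -1.6 to -4.1 with frailty variance 2. A true rate ratio of 1.29 would be masked on average.

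The follow-up imbalance comes straight from the documents. The direction rests on equal, roughly constant background rates. The size rests on rates the documents do not give and on events not driven by doses. The consequence is a risk of misreading a supportive, descriptive estimate. It does not invalidate the safety analysis or any primary conclusion.

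**What to change.** In Section 9.6.2 and Table 10, or in the supplemental SAP that Section 9 allows for nonconfirmatory changes before database lock:

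- Keep the planned MAAE proportions and M&N interval.
- Beside them, as a supportive analysis, report participants with a first MAAE per 100 person-months by group, with time counted to the first MAAE or the end of participation. Give the between-group rate difference and a 95% CI by a named method, for example a score-based interval for a difference of Poisson rates.
- Show total person-time by group.
- Footnote all three any-time rows (MAAEs, adverse events of special interest, vaccine-related SAEs) with the unequal follow-up of about 7 vs 9 months. No separate rate interval is requested for adverse events of special interest.

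The cost is one extra table, a footnote and a short piece of text. It needs the dates of each participant's first MAAE and last contact, which the AE and visit records should hold; no visit or procedure changes. The downside is over-correction of purely dose-driven events, so the rate should stand beside the proportion and never replace it. Cutting both groups at a common 7 months is less suitable, because it would leave out the period around the Nonconcomitant Group's Month 8 dose.

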3 HYPOTHESES, OBJECTIVES, AND ENDPOINTS

The following objectives and endpoints will be evaluated in boys and girls 9 to 11 years of age.

Primary Objective	Primary Endpoint

Objective 1: To evaluate the GMTs of antibodies to each of the 9vHPV vaccine types at 4 weeks Postdose 2 of a 2-dose regimen of 9vHPV vaccine, when the first dose of a 2-dose regimen of 9vHPV vaccine is administered concomitantly or nonconcomitantly with a first dose of a 2-dose regimen of mRNA-1273 vaccine.	
Serum antibody titers at 4 weeks Postdose 2 of 9vHPV vaccine measured by cLIA to each of the 9vHPV vaccine types (HPV 6, 11, 16, 18, 31, 33, 45, 52, and 58)

Objective 2: To evaluate the GMCs of SARS-CoV-2 spike protein-specific binding antibody at 4 weeks Postdose 2 of a 2-dose regimen of mRNA-1273 vaccine, when the first dose of a 2-dose regimen of mRNA-1273 vaccine is administered concomitantly or nonconcomitantly with a first dose of a 2-dose regimen of 9vHPV vaccine.	
Serum antibody concentrations at 4 weeks Postdose 2 of mRNA-1273 vaccine measured by ECL assay specific to the SARS-CoV-2 spike protein

Objective 3: To evaluate the safety and tolerability of 2-dose regimens of 9vHPV and mRNA-1273 vaccines where the first dose of each vaccine is administered concomitantly.	
Solicited injection-site AEsSolicited systemic AEsSAEsVaccine-related SAEs
Secondary Objectives	Secondary Endpoints

Objective: For each of the Concomitant and Nonconcomitant Groups, to estimate percent seroconversion to each of the 9vHPV vaccine types at 4 weeks Postdose 2 induced by a 2-dose regimen of 9vHPV vaccine.	
Serum antibody titers at 4 weeks Postdose 2 of 9vHPV vaccine measured by cLIA to each of the 9vHPV vaccine types (HPV 6, 11, 16, 18, 31, 33, 45, 52, and 58)

Objective: For each of the Concomitant and Nonconcomitant Groups, to estimate percent seroresponse at 4 weeks Postdose 2 induced by a 2-dose regimen of mRNA-1273 vaccine.	
Serum antibody concentrations at 4 weeks Postdose 2 of mRNA-1273 vaccine measured by ECL assay specific to the SARS-CoV-2 spike protein
---	---

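### Severe systemic AEs have no between-group CI and no windowed summary in Table 10, although severe injection-site AEs have both

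*Combined protocol and SAP*

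**What the plan says.** Section 3 states the third primary objective as "To evaluate the safety and tolerability of 2-dose regimens of 9vHPV and mRNA-1273 vaccines where the first dose of each vaccine is administered concomitantly".

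Section 9.6.2 divides safety endpoints into tiers. Tier 2 gets a Miettinen and Nurminen (M&N) 95% CI for the difference between groups. For Tier 3, "Only point estimates (counts and percentages) by vaccination group are provided for Tier 3 safety parameters".

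- **Injection-site severity.** The Tier 2 text says that "severe injection-site AEs during Days 1 through 28 postvaccination will also be included in Tier 2 endpoints", and Table 10 carries the matching row, "Severe injection-site AEs, Days 1 through 28 postvaccination". Tier 3 repeats the endpoint for Days 1 to 15.
- **Systemic occurrence.** Table 10 has a Tier 2 row "Solicited systemic AEs (headache, fatigue, myalgia, arthralgia, nausea, vomiting, and chills), Days 1 through 7 postvaccination", and another for unsolicited systemic AEs seen in at least 4 participants over Days 1 to 28. Neither has a severity cut.
- **Systemic severity.** There is one row, in Tier 3: "Maximum intensity rating, overall systemic AEs". Its injection-site counterpart is "Maximum intensity rating for each category of injection-site AEs". Neither row states a day range.

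Section 10.3.4 has the investigator grade the intensity of every reported AE.

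**The concern.** The two vaccines are injected into opposite arms (Section 8.1.9), so local reactions are recorded separately for each vaccine. Systemic reactions are where the effects of two same-day vaccines could combine. Yet the plan contrasts severity for local reactions only and gives no reason for the difference.

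An any-grade contrast cannot show a move up the grading scale. If coadministration turned mild systemic reactions into severe ones and left the share of children with any reaction unchanged, both systemic Tier 2 rows would look the same in the two groups. The one row that records intensity has no CI, no stated period and no separation of solicited reactions from other illness.

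**Working it through.** **1. The plan's rows side by side (Table 10).**

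| Endpoint | Tier | Window | CI |
|---|---|---|---|
| Injection-site, solicited, any grade | 2 | Days 1-7 | yes |
| Injection-site, severe | 2 | Days 1-28 | yes |
| Injection-site, severe | 3 | Days 1-15 | no |
| Systemic, solicited, any grade | 2 | Days 1-7 | yes |
| Systemic, unsolicited, any grade, at least 4 participants | 2 | Days 1-28 | yes |
| Systemic, severe | none | none | none |
| Systemic, worst grade | 3 | not stated | no |

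**2. What other rows could catch (grading tables, Section 10.3.4).**

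- Grade 4 solicited systemic reactions involve an emergency department visit or hospitalization, so they should largely reach the MAAE or SAE rows, which have CIs.
- Grade 3 nausea and vomiting include outpatient IV hydration, and Grade 3 chills include medical intervention. Many of these would also count as MAAEs.
- Grade 3 fatigue, myalgia and arthralgia are defined by preventing daily activity, and headache can qualify the same way. No medical contact is needed, so these can miss both rows.
- Fever is covered separately: elevated temperature has a Tier 2 CI, and maximum temperature is summarized.

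The gap is therefore mainly Grade 3 headache, fatigue, myalgia and arthralgia without medical care.

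**3. What the Tier 3 row may contain.** Section 8.4 collects all AEs for 28 days after each vaccination. It also says "All MAAEs, SAEs, and other reportable safety events that occur from the time of allocation/randomization throughout the duration" of participation must be reported. The synopsis gives participation as about 7 or 9 months; the schedules put the last visit at Month 7 (Concomitant) and Month 9 (Nonconcomitant). If the row covers the whole study, late MAAEs and SAEs enter it over unequal follow-up. If it covers only the post-vaccination windows, they do not. The plan does not say which.

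**4. The plan's own figure.** Section 9.6.2 sets the Tier 2 threshold at 4 participants because the CI always includes zero when equal groups each have fewer. M&N at 80 per group, with the N/(N-1) variance factor:

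- 3/80 vs 0/80: 3.75 points, CI -0.95 to 10.48 (includes zero).
- 4/80 vs 0/80: 5.0 points, CI 0.28 to 12.19 (excludes zero).

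The threshold reproduces at this group size.

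**5. What a severe systemic contrast would look like.** The documents give no rate, so these counts are assumptions.

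| Concomitant vs Nonconcomitant, of 80 | Difference (points) | M&N 95% CI |
|---|---|---|
| 8 vs 4 | 5.0 | -3.6 to 14.3 |
| 12 vs 4 | 10.0 | 0.7 to 20.2 |
| 16 vs 8 | 10.0 | -1.2 to 21.4 |

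**6. Effect of mixing in other severe events (illustration only).** With a severe reaction rate p and an equal independent background b in both groups, the mixed rate is 1-(1-p)(1-b). Take p = 12/80 = 15% vs 3/80 = 3.75%, a difference of 11.25 points (CI 2.4 to 21.2).

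- b = 5%: 1-0.85×0.95 = 19.25% and 1-0.9625×0.95 = 8.56%, about 15 vs 7 of 80. CI -0.7 to 21.1.
- b = 10%: 1-0.85×0.90 = 23.5% and 1-0.9625×0.90 = 13.4%, about 19 vs 11 of 80. CI -2.2 to 22.2.

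**7. Vaccination visits pooled by any post-vaccination row.** Concomitant: Day 1, Month 1 and Month 6, so 3 visits and 3×7 = 21 days at risk. Nonconcomitant: Day 1, Month 1, Month 2 and Month 8, so 4 visits and 4×7 = 28 days. Coadministration occurs at one visit, Day 1.

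**The case against.** A reader might infer that severe systemic reactions cannot be compared or recovered at all. The documents do not support that. Tier 3 gives counts and percentages by group, so worst systemic grade can be compared descriptively, and an M&N interval can be computed from those counts. Every AE is graded, so a windowed count needs only a definition. What the row cannot supply is the window or the individual systemic term.

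A reader might also infer that late illness is certain to contaminate the row. That reads a whole-study window into silence. The footnote to the other-systemic grading scale in Section 10.3.4 ties grading to eVRC information during the primary safety follow-up period and, beyond it, mentions only SAEs. Grade 3 for other illness requires both prevented activity and medical intervention, which limits the background.

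Third, a reader might use the formula in step 6 to measure the gain from a new row. For a true 15% vs 3.75%, the chance that the CI lies above zero is about 71% with b = 0, 50% at b = 5%, 38% at 10% and 24% at 20%. No such background rate stands in the documents, and the comparison is not like for like. Severe reactions to the later doses, given alone in both groups, enter a Days 1 to 7 row just as b does. If they occurred in 10% of each group, the same 38% would apply to the new row.

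It is also fair to say that systemic severity is not a named primary safety endpoint, that Tier 2 intervals are descriptive, and that the injection-site maximum-intensity row lacks a day range too. All of this stands. It lowers the weight of the point but does not remove the asymmetry: severe injection-site AEs have windowed rows of their own, and severe systemic AEs have none.

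**Conclusion.** The point holds in a limited form. No between-group CI and no windowed summary is prespecified for severe systemic AEs, and the single systemic intensity row leaves its period open. What goes uncontrasted is chiefly Grade 3 headache, fatigue, myalgia or arthralgia that prevents activity without medical care. That bears directly on the tolerability objective.

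The size cannot be fixed from the documents. Under assumed counts, differences of 5 to 10 points come with intervals about 18 to 23 points wide at 80 per group, so the added row would describe and would rarely settle the question. The wording of Table 10, Section 9.6.2 and the grading tables establishes the gap; the assumed rates are illustration only. This is a cheap improvement to an estimation study and does not invalidate the safety analysis. It is best made before database lock, because the trial is open-label and a severity cut chosen later would be post hoc.

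**What to change.** Add to Tier 2, in Table 10 and in the Section 9.6.2 text: *Solicited systemic AEs of Grade 3 or higher, Days 1 through 7 postvaccination*, with counts, percentages and the M&N 95% CI for Concomitant minus Nonconcomitant. List it by name, as severe injection-site AEs are, so that it does not depend on the 4-participant threshold. Give the Tier 3 systemic maximum-intensity row a stated range of Days 1 through 28 postvaccination.

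This takes one row, one sentence and one day range, with no new data or participants. The downside is one more unadjusted descriptive interval with few events; with fewer than 4 cases in each group it will include zero. Like the existing Tier 2 rows, the new row pools three visits against four, so it dilutes the Day 1 coadministration effect. The report should say so when interpreting it.
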